2 RATIONALE

- The routinely used and internationally recognised diagnostic test for assessing the requirement of ambulatory oxygen, Max_6MWT may not correspond to the degree of exercise that patients actually perform when they would use their prescribed ambulatory oxygen (i.e. normal walking speed).
- It is possible that a significant proportion of patients prescribed ambulatory oxygen cannot physiologically benefit from using it as they do not experience a decline in oxygen levels during their normal physical exercise.
- Prescribing of ambulatory oxygen to patients that cannot benefit from it carries additional burdens for the patient, and costs for the NHS, without improving the patient's quality of life.
- If this study shows that a normal walking speed test is a more appropriate assessment for ambulatory oxygen, a higher proportion of patients prescribed ambulatory oxygen will benefit from the therapy and reduce incorrect prescribing of ambulatory oxygen.
- Max_6MWT is a maximal exercise test for most patients with notable respiratory disease and is not always well tolerated (e.g. becoming very breathless). Furthermore, it carries a small but not insignificant risk of acute heart issues and falls. A 6 minute or shorter test at normal walking speed would be safer and easier for a patient to perform.
- Patients' wellbeing could be harmed by misdiagnosing exercise-induced hypoxaemia. Anecdotal evidence suggests some patients become less active after being prescribed ambulatory oxygen for a variety of reasons, including feeling self-conscious or struggling to carry the oxygen cylinder.
- Furthermore, patients may be worried about exercising without ambulatory oxygen if prescribed this therapy due to the perception of risk due to exercise-induced hypoxaemia and potentially incorrect requirement for supplemental oxygen.
- Patients who demonstrate exercise-induced hypoxaemia during a Max_6MWT are required to repeat the Max_6MWT at least once in order to identify the required flow rate of ambulatory oxygen. Titrating the flow of ambulatory oxygen is required to ensure it is sufficient to prevent the exercise-induced hypoxaemia but not too high that could induce hypoventilation and subsequent CO₂ retention. It is plausible that prescribing a flow rate shown to prevent hypoxaemia during a Max_6MWT could far exceed that required to prevent

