4.1 Objectives

Primary objective:

1. Average drop in SpO₂ from baseline to nadir

Secondary objectives:

1. Average SpO₂ during the 6 minutes walking
2. Nadir in oxygen saturation (SpO₂)
3. At what time does the nadir in SpO₂ occur during a Nor_6MWT

Other objectives:

1. Walking speed: Distance walked divided by 6 minutes
2. Average HR during the 6 minutes walking
3. Peak HR
5. Borg Scores
6. Results from questionnaires (for patient's prescribed ambulatory oxygen)

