The aim of this test is to walk as far as possible for 6 minutes. You will walk along this hallway between the markers, as many times as you can in 6 minutes.

I will let you know as each minute goes past, and then at 6 minutes I will ask you to stop where you are. 6 minutes is a long time to walk, so you will be exerting yourself. You are permitted to slow down, to stop, and to rest as necessary, but please resume walking as soon as you are able.

Remember that the objective is to walk as far as possible for 6 minutes, but don't run or jog. "

Step 3: Very slow walk to the start line and then perform the walk test.

Step 4: Perform post-test Borg score immediately after the test. Twenty minutes of rest, or a minimum of 10 minutes sitting rest/recovery with a return to baseline of SpO₂, HR and Borg Score

Step 5: Proceed to perform Nor_6MWT as above but with the following instructions: "

The aim of this test is to walk at your normal walking speed for 6 minutes. This could be the speed that you walk a dog if you have one, or the speed you would walk around town shopping. You will walk along this hallway between the markers for 6 minutes.

I will let you know as each minute goes past, and then at 6 minutes I will ask you to stop where you are. 6 minutes is a long time to walk, so you will be exerting yourself. You are permitted to slow down, to stop, and to rest as necessary, but please resume walking as soon as you are able.

Remember that the objective is to walk at your normal walking speed for 6 minutes, but don't run or jog."

Step 6: Perform post-test Borg score immediately after the test. Allow the patient to rest for at least 10 minutes or until SpO₂ and HR back to baseline.

.....

Group 2: Nor_6MWT followed by Max_6MWT.

Step 1: Wait at least 10 minutes in a seated position from any previous breathing tests. Baseline blood pressure, heart rate and oxygen saturation obtained. Borg score completed.

Step 2: Instructions provided: "

The aim of this test is to walk at your normal walking speed for 6 minutes. This could be the speed that you walk a dog if you have one, or the speed you would walk around town shopping. You will walk along this hallway between the markers for 6 minutes.

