I will let you know as each minute goes past, and then at 6 minutes I will ask you to stop where you are. 6 minutes is a long time to walk, so you will be exerting yourself. You are permitted to slow down, to stop, and to rest as necessary, but please resume walking as soon as you are able.

Remember that the objective is to walk at your normal walking speed for 6 minutes, but don't run or jog."

Step 3: Very slow walk to the start line and then perform the walk test.

Step 4: Perform post-test Borg score immediately after the test. Twenty minutes of rest, or a minimum of 10 minutes sitting rest/recovery with a return to baseline of SpO₂, HR and Borg Score

Step 5: Proceed to perform Max_6MWT with the following instructions: “

The aim of this test is to walk as far as possible for 6 minutes. You will walk along this hallway between the markers, as many times as you can in 6 minutes.

I will let you know as each minute goes past, and then at 6 minutes I will ask you to stop where you are. 6 minutes is a long time to walk, so you will be exerting yourself. You are permitted to slow down, to stop, and to rest as necessary, but please resume walking as soon as you are able.

Remember that the objective is to walk as far as possible for 6 minutes, but don't run or jog.”

Step 6: Perform post-test Borg score immediately after the test. Allow the patient to rest for at least 10 minutes or until SpO₂ and HR back to baseline.

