8 ETHICAL AND REGULATORY CONSIDERATIONS

This research aligns with both ethical and regulatory framework, aiming to improve the quality of care for patients and providing better diagnostic tools. The research poses very low risk to patients participating as they are only required to walk at their normal walking pace on a flat surface and whilst there may be no immediate direct benefit, there is a direct implication for future clinical decision making based on the outcomes of this study.

Collection of physiological data is done with non-invasive methods and respects the dignity of patients participating in the study. These collection techniques are internationally recognised and conform to all local and national legislation.

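### The normal-pace script repeats the maximal test's exertion line in both sequences, which is inconsistent with a normal-speed aim and may affect pace

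*Combined protocol and SAP*

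**What the plan says.** Section 5.1 sets out the instructions for each walk. The Nor_6MWT script appears twice, at Group 1 Step 5 and Group 2 Step 2, with the same wording. It opens with "The aim of this test is to walk at your normal walking speed for 6 minutes", gives everyday pace anchors ("This could be the speed that you walk a dog if you have one, or the speed you would walk around town shopping") and closes with "Remember that the objective is to walk at your normal walking speed for 6 minutes, but don't run or jog". Between the anchors and the closing reminder it includes "6 minutes is a long time to walk, so you will be exerting yourself". The Max_6MWT script, at Group 1 Step 2 and Group 2 Step 5, has that same sentence in the same position.

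Elsewhere the protocol presents the normal-pace walk as undemanding. Section 2 argues that the maximal test "may not correspond to the degree of exercise that patients actually perform when they would use their prescribed ambulatory oxygen (i.e. normal walking speed") and expects a normal-speed test to be lower in risk and less taxing. Section 8 says of participants that "they are only required to walk at their normal walking pace on a flat surface".

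Section 4.1 makes the SpO₂ drop from baseline to nadir the primary objective. It lists "Walking speed: Distance walked divided by 6 minutes" among the other objectives.

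**The concern.** Section 1 says both walks use the same equipment and the same location. Group 1 Step 5 then runs the normal-pace walk like the maximal one, apart from the instructions. The script is therefore the experimental manipulation, and effort is the thing it is meant to change. A sentence telling the patient to expect exertion, common to both conditions, works against that purpose.

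Two things are at stake. The first is representativeness: the case for the Nor_6MWT rests on its reflecting the pace at which patients would use ambulatory oxygen. The second is the primary contrast: if the cue speeds up the normal-pace walk, the two conditions move closer together.

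Clear wording matters in this population. In Appendix 4 the patient group reported having been asked to walk at different speeds by different staff, and being unsure what the tests were for.

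**Working it through.** The plan gives no figure for pace or for the effect of wording on pace, so there is nothing to reproduce. The check is a comparison of the two scripts in section 5.1, element by element.

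| Element | Max_6MWT | Nor_6MWT (both groups) |
|---|---|---|
| Opening aim | Greatest possible distance | "The aim of this test is to walk at your normal walking speed for 6 minutes" |
| Pace anchor | None | "This could be the speed that you walk a dog if you have one, or the speed you would walk around town shopping" |
| Course instruction | Between the markers, "as many times as you can in 6 minutes" | Between the markers for the six minutes; effort phrase removed |
| Minute calls and stop signal | Present | Identical |
| Exertion line | "6 minutes is a long time to walk, so you will be exerting yourself" | Identical |
| Leave to ease off, halt or rest, then resume | Present | Identical |
| Closing reminder | Greatest distance, no running | "Remember that the objective is to walk at your normal walking speed for 6 minutes, but don't run or jog" |

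**Step 1: is the line there, and in both sequences?** Yes. Both sequences receive the same Nor_6MWT wording, so the line creates no difference in instruction between them.

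**Step 2: does it fit the aim?** The other effort-related elements (aim, anchor, course instruction, closing reminder) were adapted for the normal-pace test. The exertion line sits in a middle paragraph that was left unchanged. It fits poorly with the section 2 and section 8 descriptions of the test.

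**Step 3: what would follow?** Let D = (SpO₂ drop in Max_6MWT) − (SpO₂ drop in Nor_6MWT), and take the protocol's premise that faster walking desaturates more.

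- If the line raises Nor_6MWT pace, the second term grows and D falls.
- If it makes patients pace more cautiously, the second term shrinks and D rises.
- In either case the Nor_6MWT moves away from everyday pace.

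Nothing in the documents says which of these occurs, or by how much.

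**Step 4: can the trial detect it?** In part. Distance divided by six minutes, compared between tests, shows whether the two paces separated. It cannot show that the Nor_6MWT pace was the patient's usual one, because no measure of everyday walking speed is collected. The IPAQ Elderly Short questionnaire is collected, but section 5 uses it to judge benefit from oxygen and does not present it as a measure of pace.

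**The case against.** The strongest case for leaving the script alone has five parts.

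- **The line is a warning.** It does not ask for more effort, and permission to ease off follows at once. It could slow some patients. This stands: the direction of any effect is open.
- **Normal speed is stated before and after it.** The anchors help, and the closing reminder comes later than the disputed sentence. This stands as partial mitigation.
- **The line may simply be true.** Section 1 describes patients referred with breathlessness on exertion, for whom six minutes at ordinary pace can be an effort. Keeping the shared paragraph identical is also a defensible design choice. This stands in part, but a true statement can still cue effort, and effort is the variable being manipulated.
- **Published guidance.** Appendix 3 says the 6MWT instruction was amended to match it, without saying which script or sentence changed. That could support the line in the standard test. It gives little support in the normal-pace test, since section 2 reports no published adaptation for ambulatory oxygen assessment.
- **Walking speed is already recorded.** This stands for separation between the tests, but not for whether the normal pace was truly normal.

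A reader might go further and infer that the line does push the normal-pace walk toward the maximal one, and that power at 82 patients suffers by some calculable amount. The documents do not support this. Any percentage loss would be invented. Section 7.2.1 ties its effect size of 0.30 to SpO₂ at rest and at the end of the walk, and does not define it as the Max-minus-Nor difference in drop to nadir. The pilot's script is not given either; if it contained the same line, any effect is already in the 0.30.

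A reader might also infer a stronger cue in Group 1, where the normal-pace walk follows a maximal one. Nothing in the documents shows that, and the fresh comparison could equally make the difference in pace clearer.

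**Conclusion.** The point holds as an inconsistency in the manipulated variable, with a possible but unmeasured consequence. It is certain from the text that the exertion line is in both Nor_6MWT scripts, that it matches the Max_6MWT line word for word, and that it fits poorly with the protocol's own account of a normal-pace test.

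The rest is conditional. If patients respond to the line by walking faster, and desaturation rises with pace, the primary difference would be reduced. The normal-speed wording around the line partly offsets this. No magnitude and no order-specific effect is claimed. The representativeness concern does not depend on the direction of the effect or on which script the pilot used. The case for changing the script rests on its low cost and the better match to the trial's question, not on a demonstrated bias.

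**What to change.** Delete the sentence "6 minutes is a long time to walk, so you will be exerting yourself" from the Nor_6MWT script at Group 1 Step 5 and Group 2 Step 2. Leave the Max_6MWT script unchanged. Keep the minute calls and the permission to ease off or rest in both scripts.

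Report walking speed for each test, and the within-patient difference, beside the primary result as a check on pace separation. State that this does not establish that the Nor_6MWT pace was the patient's everyday pace.

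The cost is one sentence removed in two places, through a protocol amendment, with no added patient burden and no new data collection. The downside is that, if recruitment has begun, two versions of the Nor_6MWT script will exist in one trial. In that case, record which version each patient heard.

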6 STUDY SETTING

This is a single centre study, taking place at two locations within HHFT: the Royal Hampshire County Hospital, Cardiac Measurement Department and at Basingstoke and North Hampshire Hospital, Cardiac Investigations. These locations are current sites for standard Max_6MWT and are suitable for carrying out the additional Nor_6MWT with access to the required space and equipment for this research.

Patients will be assessed during a routine clinic appointment and the tests performed in a corridor within the respective departments.

Each location will perform the same activity.

7 SAMPLE AND RECRUITMENT

7.1 Eligibility Criteria

Patients must be attending a respiratory outpatient clinic at Hampshire Hospitals NHS Foundation Trust to be eligible for the study and meet the following criteria:

7.1.1 Inclusion criteria

1. Referred for a Max_6MWT
2. Provision of informed written consent
3. Aged 18 years or over

7.1.2 Exclusion criteria

1. Lack of capacity to provide informed consent
2. Poor peripheral perfusion that prevents an accurate measurement of SpO₂
3. Contraindicated to perform a Max_6MWT as indicated in the standard HHFT 6MWT SOP
4. Already prescribed ambulatory oxygen

7.2 Sampling

All patients referred for a diagnostic 6MWT will be informed of the study and asked if they wish to participate following reading and understanding the patient information leaflet and providing informed consent.

7.2.1 Size of sample

A sufficient number of patients will be recruited in order to assess any differences between the Max_6MWT and Nor_6MWT. The study is to establish whether there is any significant difference of the continuous variable, SpO₂, at rest and at end of 6 minute-walk. Prior data, from the HHFT pilot study, yielded an effect size of 0.30 and this study will need 82 subjects to be able to reject the null hypothesis that this response difference is null with a power of 80%. The Type I error probability associated with this test for null hypothesis is 0.05.

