4 RESEARCH QUESTION/AIM(S)

To compare the nadir in oxygen saturation reached whilst performing a standard Max_6MWT compared with a Nor_6MWT.

To compare the average oxygen saturation and average drop in oxygen saturation from baseline to the nadir whilst performing a standard Max_6MWT compared with a Nor_6MWT.

To measure when the nadir in oxygen saturation occurs during a Nor_6MWT.

To assess in patients prescribed ambulatory oxygen, what benefit in their symptoms do they report and how does this compare to their Max_6MWT and Nor_6MWT results.

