4.2 Outcome

A greater drop in oxygen saturation during a Max_6MWT compared with Nor_6MWT may indicate over-prescribing of ambulatory oxygen as during normal activity, patients' requirement for oxygen may be lower than indicated by a Max_6MWT. Whilst ambulatory oxygen can improve patients' quality of life, it is not without drawbacks and, therefore, prescribing only to patients that will benefit is important.

5 STUDY DESIGN and METHODS of DATA COLLECTION AND DATA ANALYSIS

Patients attending a routine appointment for a Max_6MWT will be identified and approached to be invited to participate in the research study.

Along with a basic clinical history, the patient's blood pressure, Borg score for dyspnoea and leg fatigue, oxygen saturation and heart rate will be recorded before the walk tests – their baseline measurement.

The order of the tests will be randomised using a random number generator on the day where odd numbers will perform a Max_6MWT followed by a Nor_6MWT and even numbers the reverse. For each test, clear instructions will be provided along with continuous monitoring of their oxygen saturation heart rate and distance walked for the 6 minutes of the test using a using a Bluetooth enabled device that transmits this data to a medically approved monitoring device with manual lap counting. Should this equipment fail, manual readings will be taken every minute during the test.

Between each test, ample time (usually 20 minutes) will be provided for a patient's degree of dyspnoea and leg fatigue, and objective measurements of heart rate and oxygen saturation to return to baseline.

From these tests it is possible to determine the distance walked, the degree of dyspnoea and leg fatigue, the time to nadir in oxygen saturation, the average drop in oxygen saturation and the average and peak heart rate. These data can be compared using paired tests to determine differences between Max_6MWT and Nor_6MWT.

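### The 80% power in Section 7.2.1 is tied to end-of-walk SpO₂ and is not shown to apply to the primary comparison, the Max-versus-Nor difference in baseline-to-nadir drop

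*Combined protocol and SAP*

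**What the plan says.** Section 7.2.1 opens with the purpose of the sample size: "A sufficient number of patients will be recruited in order to assess any differences between the Max_6MWT and Nor_6MWT". It then gives the question to be answered as "whether there is any significant difference of the continuous variable, SpO₂, at rest and at end of 6 minute-walk". The only input from earlier work is described in these words: "Prior data, from the HHFT pilot study, yielded an effect size of 0.30". From this the section derives a requirement of 82 patients for 80% power, with alpha set at 0.05. It does not give the kind of effect size, the pilot mean and SD, the test or its sidedness.

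Section 4.1 names one primary objective: "Average drop in SpO₂ from baseline to nadir". Section 4.2 shows that the comparison of interest is between tests: "A greater drop in oxygen saturation during a Max_6MWT compared with Nor_6MWT may indicate over-prescribing of ambulatory oxygen". Section 5 says the data can be compared by paired tests. Among the secondary objectives in Section 4.1 is "At what time does the nadir in SpO₂ occur during a Nor_6MWT". Section 7.3 removes any patient who cannot complete both walks, and Section 7.2.1 makes no allowance for this.

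**The concern.** The variable in the sample-size paragraph is not the primary variable. One uses the reading at the end of the walk and the other uses the lowest reading during it. The protocol cannot treat these as the same, because it lists the time of the nadir in the normal-speed walk as something to be found out. The walk instructions in Section 5.1 also let patients slow down, stop and rest, so SpO₂ may recover before the sixth minute.

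Section 7.2.1 is the only quantitative justification for 82 patients, and Section 4.2 draws an implication for prescribing from a larger drop on the maximal walk. If power for that comparison is unknown, a non-significant result will be hard to interpret. It could mean that the tests agree, or that the trial was too small to separate them.

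**Working it through.** **1. The two variables side by side.** For one walk, let E be rest minus end-of-walk SpO₂, N be rest minus nadir, and R be end-of-walk minus nadir, so R ≥ 0. Then N = E + R. The between-test difference in the primary variable is

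N(Max) − N(Nor) = [E(Max) − E(Nor)] + [R(Max) − R(Nor)].

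The last bracket can be positive or negative, and it also changes the SD of the difference. An effect size for the end-of-walk quantity therefore does not carry over to the nadir quantity. The protocol gives no figures from which to judge which way it moves.

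**2. Can the plan's 82 be reproduced?** Inputs from Section 7.2.1 are effect size d = 0.30, alpha 0.05 and power 80%. Assume, favourably, that 0.30 is the mean within-patient difference divided by its own SD, for the primary variable.

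- Normal approximation, two-sided: n = ((1.960 + 0.842)/0.30)² = 87.2, so 88.
- Exact paired t, two-sided: 90.
- One-sided: 69 (normal) or 71 (t).

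None of these is 82. Rounding of the effect size does not explain it: values from 0.295 to 0.305 give 93 down to 87 with the two-sided t-test. Exactly 82 does come from two methods that the protocol does not mention. One is a one-sided Wilcoxon signed-rank test with asymptotic relative efficiency 0.864 (power 80.4%). The other is a two-sided point-biserial correlation of 0.30 (power 80.3%).

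**3. Power at 82 on the favourable reading.** The noncentrality is 0.30 × √82 = 2.717 on 81 degrees of freedom. Power is 76.6% two-sided and 85.3% one-sided. The smallest effect with 80% power at 82 is about (1.960 + 0.842)/√82 = 0.309 by the normal approximation, and 0.313 SD by the exact two-sided t-test.

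**4. Non-completers.** The loss rate is an assumption, because the protocol gives none. With d = 0.30, two-sided paired t:

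| Assumed loss | Completers | Power |
|---|---|---|
| 0% | 82 | 76.6% |
| 5% | 77 | 73.9% |
| 10% | 73 | 71.5% |
| 20% | 65 | 66.4% |

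**5. If the paired effect for the primary variable is not 0.30.** These effects are assumed, with the same test and 82 completers:

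| Standardised paired difference | Power at 82 | N for 80% |
|---|---|---|
| 0.20 | 43% | 199 |
| 0.25 | 61% | 128 |
| 0.30 | 77% | 90 |
| 0.35 | 88% | 67 |
| 0.40 | 95% | 52 |

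**The case against.** The best defence is that Section 7.2.1 is loosely worded and not misdirected. Its first sentence refers to differences between the two tests, its null hypothesis concerns a response difference, and Section 5 plans paired comparisons between tests. A natural reading is that the response is the change from rest, and that the response difference is Max versus Nor. If 0.30 is that paired effect, power at 82 is about 77%, not far from the stated 80%. A one-sided 5% test would exceed 80%.

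Much of this stands. A reader might infer from the rest-versus-end wording that the trial is powered only for a change within one walk, and so for a hypothesis it never tests. The opening sentence does not allow that to be stated as fact. A reader might also infer that true power is far below 80%. The documents do not support this either: the primary variable has no stated effect size, and power could equally be higher.

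Nor does Section 4 supply a rival primary outcome. Its first aim is "To compare the nadir in oxygen saturation reached whilst performing a standard Max_6MWT compared with a Nor_6MWT", but the list is unranked and its second aim includes the drop to nadir. Section 4.1 then names a single primary objective and puts the nadir itself among the secondary ones.

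The defence does not remove the mismatch of variable. On the between-test reading, the powered quantity is still measured at the end of the walk.

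**Conclusion.** The concern holds as an inconsistency between Sections 7.2.1 and 4.1 and as a gap in the justification of the sample size. The stated 80% power is attached to an end-of-walk quantity and is not shown to apply to the between-test difference in baseline-to-nadir drop. The direction of any error cannot be determined from the documents.

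On the favourable assumption that 0.30 is the standardised within-patient difference for the primary variable, a two-sided paired t-test at 5% gives 76.6% power with 82 completers and needs 90 for 80%. That is before patients are removed for not completing both walks. The shortfall depends on the two-sided test, which the protocol does not specify. The figure of 82 is therefore unexplained, not proven wrong.

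**What to change.** Rewrite Section 7.2.1 for the primary variable: the mean within-patient difference, Max minus Nor, in the drop in SpO₂ from baseline to nadir. State what the pilot measured, whether each pilot patient did both walks, and what the 0.30 refers to, including the SD used to scale it.

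- If the pilot has paired nadir data, quote the mean and SD of that difference and the resulting power at 82, naming the test and its sidedness.
- If it does not, say so. Replace the 80% claim with the detectable difference, 0.313 SD of the within-patient difference at 80% power (two-sided paired t, 5%, 82 completers).

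In either case, make clear that the figure refers to patients who complete both walks. Reconcile the end-of-walk wording with the nadir definition and do not simply delete it, because it may be the only record of how the pilot effect size was obtained.

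The cost is rewording, plus a short re-analysis if the pilot recorded paired nadirs. No study procedure changes. The downside is that the restated power may be less favourable than 80%.
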